#### Human Subjects Involvement and Characteristics:

**Participants:** Participants will be individuals age 18 - 85 with and without PD from the Atlanta VAMC as well as other communities. During fiscal year 2010, 500 veterans with PD were seen at the Atlanta VAMC and satellite clinics. As VA funded research is conducted for the benefit of veterans, we will prioritize their recruitment by first exhausting all available means by which we can identify, approach and recruit veterans for this study. After we exhaust all possible resources to recruit veterans with PD, we anticipate extending recruitment to university based movement disorders clinics and community clinics. We will do so because we intend to recruit 140 participants with PD, and 40% will be women, which reflects female representation in the PD population. The greater Atlanta region had 650,000 people age 55 and over in the 2000 US Census (US Census Bureau). As the older population is expected to double by 2015, and given a PD prevalence of 1.5% of the population age 65 and older, we estimate there to be more than 4000 people with PD in the greater Atlanta area. Emory University, the Atlanta VAMC affiliate, has a Movement Disorders unit that follows more than 2000 patients with PD each year.

We are targeting those aged 40-85 with stages II and III. Forty is the upper limit for young onset PD, which will effectively insure that we recruit individuals with idiopathic PD only. Eighty five years is an upper age limit because of vascular, hemodynamic, morphometric and neural changes with aging. A prior study conducted by the PI involved 78 individuals with PD, 70% of whom were under the age of 70 and 83% were stages II-III, which suggests that our intended recruitment for an intervention will be attainable.

**Table 4: Inclusion/Exclusion Criteria for All Participants (Controls and those with PD)**

Inclusion	Exclusion

• Age 18 - 85 years

• Willingness to spend 1-h in a scanner

• Able to walk with or without an assistive device <math>\geq</math>10 feet

	

• Deep brain stimulator implants, Metallic implants, fragments, or pacemakers

• MoCA score < 21

• Pure-tone threshold sensitivity > 40 dB

---

 
• Best corrected/aided acuity better than 20/70 in the better eye
 
• Absence of dementia or vascular cognitive impairment
 
• Absence of primary memory deficits
 
	
 
• Peripheral neuropathy
 
• Untreated Major Depression
 
• History of stroke, or traumatic brain injury
 

---	---

---

**Inclusion/Exclusion Criteria for Participants without PD (Controls):** In addition to the criteria noted in table 2, these participants must not have PD.

**Inclusion/Exclusion Criteria for Participants with PD:** In addition to the criteria noted above in Table 2, **participants with PD** must have clinical diagnosis of “definite PD”, based upon established criteria, and must have presented with asymmetric symptoms that included at least 3 of the cardinal signs of PD (rigidity, bradykinesia, tremor, postural instability). Each PD participant also must show clear symptomatic benefit from PD medications, e.g., levodopa.

## 7. Statistical Analyses

**Power Analysis for Specific Aim 1:** We anticipate that 20 participants in each group (total n=40) will be necessary to detect an adequate effect size at 80% power based on studies conducted to determine reasonable sample sizes for fMRI studies. Twenty-four participants per group will be recruited to accommodate 20% attrition. Analysis of variance (ANOVA) will be used to determine and distinguish circuits involved in IG and EG foot-tapping networks in participants with and without PD. The ANOVA will be sensitive to between subjects effect sizes of  $f=0.45$  ( $F_1, 38= 4.098$ ), with a power of 0.80 at  $\alpha=.05$ .

### **Statistical Analysis Plan for Aim 1**

- **Participant characteristics:** Descriptive statistics will describe groups, including disease severity and duration for those with PD. T-tests will compare means (e.g., age, mental status) of participants with and without PD. Data analyses will be completed in SPSS (v. 19).
- **Functional performance measures:** Foot-tapping absolute timing error and average amplitude will be compared between groups with t-tests. These measures will also be correlated to fMRI data.
- **fMRI Brain Activation Analyses:** Following preprocessing and normalization to standard space, activation maps for the IG and EG tasks versus rest will be determined for each subject on a voxel by voxel basis. Regressors of interest will model IG and EG blocks of foot movement for each limb separately. Head motion parameters will be included as additional regressors. A similar approach has been used previously in PD. First level contrast maps (betas) for the IG and EG tasks versus rest derived in each subject will be submitted to a second-level, random-effects analysis with subject as a random factor. Second-level t-maps will be thresholded at  $p <.05$ , corrected for multiple comparisons using the false discovery rate (FDR) method. These activation maps will be used to define circuitry for IG and EG foot-tapping. Average percent signal change for the IG and EG tasks (relative to rest) for each participant will be extracted from the centers of gravity of the activated regions and submitted to hierarchical regression analyses to determine whether they correlate with behavioral measures (absolute timing errors and average amplitude of foot-tapping). Disease severity and duration of illness will be covariates for individuals with PD. **The primary outcome measure will be average percent signal change** for the IG and EG tasks (relative to

rest) to determine and distinguish circuits involved in IG and EG foot-tapping networks in participants with and without PD.

## Power Analyses for Aim 2

**Hypothesis 1:** Power calculations for Aim 2 are based upon an assumed 4-point improvement and effect sizes  $> 0.8$  on the BBS after 12 weeks of adapted tango, which was attained previously (see Preliminary Studies), and the minimal detectable change on the BBS in parkinsonism is 2.84 points. Therefore, with a total sample size of 63 participants (21 participants in each of 3 groups: IG, EG, and BC) a repeated measures (RM) ANOVA with 3 levels of repeat will be sensitive to between-within interaction main effect size of  $f(v) = 0.44$  ( $F_{4,114} = 2.45$ ) with a power of 0.80 at  $\alpha=.05$ . Post hoc sensitivity to effects between groups will be  $d = 0.90$ , and within groups,  $d_z = 0.65$ . To reflect an anticipated 20% attrition, we will recruit an additional 4 participants per group. Thus we will recruit 25 participants per group, for a total of 75 individuals with PD recruited for Aim 2. **Hypothesis 2:** 25 participants per group will be sufficient to detect effects for the imaging (activation and resting state) components of Aim 2 as well, based on studies conducted to determine reasonable sample sizes for fMRI studies, that demonstrate at least 20 participants in each group are necessary. **Hypothesis 3:** Differences in RSfc have been noted between different groups of individuals with PD in sample sizes of 16 per group; therefore, with 25 individuals per group, we will be able to detect differences between groups.

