## **6. Participant Selection**

### **Recruitment and Informed consent:**

**Recruitment:** We will recruit 140 adults aged 40-85, with PD stages II-III and 24 age-matched controls. Individuals without PD (controls) will be recruited from the Atlanta VAMC RR&D CoE's registry, the VA's VINCI database, as well as at senior living communities with whom the PI has a relationship. All patient information will be stored on VA secure servers (room 3A 105) of the Atlanta VA Medical Center. Only authorized study team members will have access to this information because it will be stored on a private directory with limited access and password locked file.

We will request a partial HIPAA waiver to identify potential participants for recruitment purposes from IRB and related approvals from the local VA R&D committees. We will then obtain a list from the VA Movement Disorders clinic including patients likely to have a PD diagnosis, and send them a letter, with the director's signature informing them about the study. Drs. [name] and [name], among others, will assist. A follow-up call will be placed within two weeks of the veteran likely having received the letter. A telephone screen will determine eligibility for participating in fMRI. Also, study fliers will be posted in the medical center and a PowerPoint slide ad will be broadcast throughout the medical center closed circuit TV system, such that veteran self-referrals are possible. To aid recruitment efforts, the PI will initiate meetings with community providers to explain the research goals, and request them to send a letter describing the study to patients who may qualify and have interest. The PI and staff will also visit PD community support and educational groups to present information to potential participants. Specifically, the PI will present information about the study to potential subjects at the 10+ support groups meeting monthly, organized by the GA chapter of the American Parkinson Disease Association and other PD organizations. The PI will also draft information about the trial to be included in the APDA and other PD organizations' newsletters and informational material, as well as the Michael J Fox foxfinder website for clinical trials in PD.

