- **Brain Connectivity Analyses for Aim 2, Hypothesis 3:** In Aim 2, Hypothesis 3, we will examine RSfc for increases or decreases as a function of training type and evaluate changes for correlations with improvement on behavioral outcomes. We will use regions of interest (ROIs) informed by IG and EG foot-tapping fMRI analyses in Aim 1. Seed ROIs will be 10mm spheres around centers of gravity of clusters of activation in the group level activation maps for IG and EG foot-tapping, in STC areas (posterosuperior putamen, ventral anterolateral thalamus, rostral SMA, and primary motor cortex) and CTC areas (cerebellum Larsell lobules IV, V, and VI, ventral posterolateral thalamus, primary somatosensory cortex, and the ventral premotor cortex). Seed ROIs gained from the foot-tapping task provide one path of inquiry into neural network changes that may occur after training. As RSfcMRI analyses can be extended to other important areas of brain function, we will also use behavioral measures, which may have changed (e.g., spatial

cognition) to determine other ROIs for interrogation of changes in RSfc. For all participants, we will use Pearson's correlation ( $r$ ), to correlate the time series from the seed ROIs with the time series of all other brain voxels. R-maps will undergo Fisher's  $r$  to  $z$  transformation and will be entered into a 2nd level random effects analysis for between group comparison using one way ANOVA in SPM8. T maps will be thresholded at  $p<.005$  ( $Z>2.6$ ). Correction for multiple comparisons will be carried out at cluster level according to random fields theory. Age will be a nuisance covariate in all statistical analysis. To account for head motion-related spurious differences in functional connectivity levels, a nuisance regressor based on the total amount of movement will be included in the design. To determine the effect of time and training status on each group, the  $z$  scores will be submitted to a 3 group (IG, EG, BC) x 2 time (pre, post) RM ANOVA. Post hoc analyses will be corrected for multiple comparisons. The **primary outcomes for Aim 2, Hypothesis 3** will be changes in average connectivity strength across STC and CTC circuits, as measured by average cross correlation coefficient between the seed regions of the circuits.

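### The non-randomised Aim 1 comparison of PD and control participants has no stated age or sex term; sex is not matched either, and the reach of the plan's one age covariate is unclear

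*Combined protocol and SAP*

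**What the plan says.** Under Statistical Analysis Plan for Aim 1, "The primary outcome measure will be average percent signal change" for the two tapping tasks relative to rest, used to distinguish circuits in people with and without PD. The model is given under Power Analysis for Specific Aim 1: "Analysis of variance (ANOVA) will be used to determine and distinguish circuits involved in IG and EG foot-tapping networks". That paragraph also sets the evaluable size, "We anticipate that 20 participants in each group (total n=40) will be necessary", and states sensitivity to f = 0.45 with 1 and 38 degrees of freedom at 80% power.

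The Aim 1 plan names two kinds of adjustment. Head-motion parameters enter the first-level model. Disease severity and duration are covariates for the PD participants, in the regressions on tapping behaviour. Timing error and amplitude are compared between groups by t-test. Age appears only under participant characteristics: "T-tests will compare means (e.g., age, mental status) of participants with and without PD".

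On design, the Recruitment paragraph of section 6 plans 140 adults "with PD stages II-III and 24 age-matched controls". Human Subjects Involvement and Characteristics says of the 140 PD recruits that "40% will be women, which reflects female representation in the PD population". No sex target is given for controls or for the 24 PD participants in Aim 1.

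The only age covariate is in the bullet Brain Connectivity Analyses for Aim 2, Hypothesis 3: "Age will be a nuisance covariate in all statistical analysis".

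**The concern.** PD and control participants are not randomised, so a characteristic that differs between them and affects the signal enters the group contrast as bias. The plan itself treats age as relevant to imaging: Human Subjects Involvement and Characteristics justifies its upper age limit by age-related vascular, haemodynamic, structural and neural change. Age is handled by matching, with no method or tolerance given. Sex is handled by neither design nor analysis.

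The groups are also recruited differently. PD recruitment may extend to university and community clinics, and the 40% target is part of the reason given. Controls come from a VA registry, a VA database and senior living communities. The plan therefore gives no assurance that the sex mix will agree.

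At stake are a modest bias in the primary Aim 1 contrast if the sex mix differs, and some lost precision if it does not.

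**Working it through.** **Inputs from the documents.** 20 evaluable per group (N = 40), f = 0.45, alpha 0.05, stated power 0.80, degrees of freedom 1 and 38.

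**Assumed inputs, because the documents give none.** Women among Aim 1 PD participants 40% (borrowed from the target for all 140 PD recruits); women among controls 10% or 20%; sex effect on the signal 0.3 to 0.8 SD; residual age difference 0.3 or 0.5 SD; age-signal correlation 0.2 to 0.4.

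**1. Reproduce the plan's figure.** For two equal groups f = d/2, and the noncentrality is λ = f² × N = 0.45² × 40 = 8.1. With 1 and 38 degrees of freedom the critical F is 4.098, as stated, and power is 0.792 against the stated 0.80. The figure reproduces. Since 38 = 40 − 2, it belongs to a two-group model with no covariate; age would leave 37, and age plus sex 36.

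**2. Bias if sex mix differs and is ignored.** Spurious d = sex effect × difference in the proportion of women. With 40% against 10% the difference is 0.30. The type I error is the rejection rate at λ = (d/2)² × 40.

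| Sex effect (SD) | Spurious d | Type I error |
|---|---|---|
| 0.3 | 0.3 × 0.30 = 0.09 | 5.9% |
| 0.5 | 0.5 × 0.30 = 0.15 | 7.5% |
| 0.8 | 0.8 × 0.30 = 0.24 | 11.5% |

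With 20% women among controls, effects of 0.3 and 0.5 SD give d = 0.06 and 0.10, and 5.4% and 6.1%. With equal sex mix, d = 0 and the error stays at 5%.

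**3. Residual age difference.** If matching left 0.5 SD, correlations of 0.2, 0.3 and 0.4 give spurious d of 0.10, 0.15 and 0.20, and type I error of 6.1%, 7.5% and 9.5%. The planned baseline t-test would have 34% power to detect a 0.5 SD age difference and 15% for 0.3 SD, so a non-significant result would not show balance.

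**4. Power with age and sex in the model (1 and 36 degrees of freedom, critical F 4.113).**

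- Balanced groups, covariates explaining nothing: 0.791 against 0.792.
- Balanced groups, covariates explaining a share R² of variance, so that f becomes 0.45/√(1 − R²): 0.831 at 10%, 0.872 at 20%.
- Unequal sex mix, covariates explaining nothing, so that f becomes 0.45 × √(1 − r²), where r² = (half the difference in proportions)² / [p(1 − p)] and p is the mean proportion of women:
  - 40% against 20%: r² = 0.10²/(0.30 × 0.70) = 0.048, power 0.771.
  - 40% against 10%: r² = 0.15²/(0.25 × 0.75) = 0.12, power 0.738.

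The last two effects offset each other. At 40% against 10% with 10% of variance explained, f is multiplied by √(0.88/0.90) = 0.99, close to no change.

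**The case against.** The strongest reply is that much of this is already covered or unproven.

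- **Age covariate.** A reader might infer that age is adjusted for only in the connectivity analysis. The text does not establish that: taken literally, the sentence covers every analysis. Its position in the Hypothesis 3 bullet, Aim 1's own covariate list and the 38 degrees of freedom favour the narrow reading, but the scope is ambiguous, not settled.
- **Age matching.** It is tempting to say that leaving age out of the model wastes the matching. It does not. Matching still limits the age difference between groups; omitting age loses precision and leaves any residual difference uncorrected.
- **Sex imbalance.** A reader might take the 40% target and the VA sources as showing that controls will have fewer women. The target is for all 140 PD recruits. The Overview and the Aim 1 plan describe both groups as veterans. Control sources are listed without weights and include senior living communities. The Informed consent paragraph rules out exclusion by sex and expects participants to mirror the metropolitan area. Imbalance is a risk, not a finding.
- **Size.** A spurious 0.09 to 0.15 SD is small beside a detectable d of about 0.9 (2 × 0.45).
- **Cost.** Adjustment is not free when the groups differ on sex.

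All of this stands, and it limits the point. It does not supply what is missing: on either reading of the age sentence, sex is neither matched nor adjusted for, and the Aim 1 section does not state a covariate-adjusted group comparison.

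**Conclusion.** The point holds as a gap in specification with a modest possible bias. As written, the Aim 1 group contrast has no age or sex term; age is matched, sex is not addressed, and the scope of the age covariate needs stating.

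Under the central assumed scenario (40% against 10% women, sex effect 0.3 to 0.5 SD) the type I error rises from 5% to between 5.9% and 7.5%. These figures rest wholly on assumed sex mixes and effects. If the groups have the same sex mix there is no sex bias, and the case for adjustment is precision alone. The change is still worth making, because it is cheap and because choosing covariates after seeing the baseline t-tests would be data-driven.

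A reader might extend the argument to the Aim 2 activation models. It does not carry over: those groups are randomised and measured before and after training, so this confounding argument does not apply.

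**What to change.** In the Statistical Analysis Plan for Aim 1, prespecify ANCOVA with group, age and sex for percent signal change, timing error and amplitude, and put age and sex in the second-level PD-control model. State explicitly that the age covariate now named in the connectivity bullet also applies to Aim 1. Preferably, in the Recruitment paragraph of section 6, frequency-match the 24 controls to the sex mix of the 24 Aim 1 PD participants as well as on age; this also protects the power of the adjusted analysis.

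The cost is SAP wording, two degrees of freedom and, with sex matching, slightly narrower control recruitment. Age and sex are basic descriptors that should need no new assessment. The planned 20 evaluable per group need not change for the lost degrees of freedom. Without sex matching, a clear imbalance could take power to 0.771 or 0.738 in the scenarios above, less whatever the covariates recover by explaining variance.

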first we will use fMRI to investigate neural correlates of lower limb control with a foot-tapping task under IG and EG conditions in veterans with and without PD (Aim 1). Imaging studies have previously employed foot-tapping, which is used clinically to assess lower limb control. To achieve Aim 2, we will 1) evaluate the relative effectiveness of practicing IG movement (leading) versus practicing EG movement (following) versus a behavioral control (health education) for improved mobility and lower limb control, and 2) assess neural activity changes underlying improvements in lower limb control across training groups. The long-term goal is to optimize motor rehabilitative interventions for veterans with PD and understand the neural mechanisms through which the training is effective in order to further improve rehabilitation strategies for this and similar diseases.

**Specific Aim 1: Determine neural correlates of internally guided and externally guided foot-tapping in individuals with and without PD.**

**Hypothesis 1:** In healthy controls, IG and EG foot-tapping are related to task-specific neural networks of the striato-thalamo-cortical and cerebello-thalamo-cortical circuits, respectively. In those with PD relative to controls, IG foot-tapping will result in increased activation of both the STC (posterosuperior putamen, ventral anterolateral thalamus, rostral supplementary motor area, primary motor cortex) and the CTC (cerebellum (Larsell lobules IV, V, and VI), ventral posterolateral thalamus, primary somatosensory cortex, ventral premotor cortex) circuits. EG foot-tapping will result in increased activation in the CTC circuit only.

**Specific Aim 2: Determine the effect, in individuals with PD, of internally guided versus externally guided training compared to a behavioral control on: 1) mobility, and 2) whether improved mobility and foot-tapping performance after training correlate with changes in activation and resting-state functional connectivity patterns in IG and EG foot-tapping networks.**

**Hypothesis 1:** If mobility gains are related to training in planning and selecting movements, then those in IG will demonstrate greater improvements than those in EG or control. If mobility gains are related to exploiting cues during training, then those in EG will demonstrate greater improvements than those in IG or control.

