#### **Rationale for hypothesized areas within circuits during IG and EG tasks:**

For **IG networks**, we expect to see activation in the following areas: the posterosuperior putamen, because dopamine depletion in PD most adversely affects this part of the putamen, which is also less functionally connected to important motor structures i.e., the rostral SMA, in individuals with PD relative to controls; the ventral anterolateral thalamus because of its projections from the basal ganglia and because it is part of the IG network outlined by Lewis et al. (2007) and Sen et al. (2010); the rostral SMA, because of its involvement in motor preparation and initiation, and its activation during foot flexion/extension; the primary motor cortex, because of its activation during foot movements and IG tasks in people with PD.

For **EG networks**, we expect to see activation in the following areas: Larsell lobules IV, V, and VI of the cerebellum, because these areas were functionally activated during cued foot movement in controls; the ventral posterolateral thalamus, because of its projections from sensory areas and cerebellar inputs, and because it is part of the circuit outlined by Lewis et al. (2007) and Sen et al. (2010); the primary somatosensory cortex, for its involvement in cued movement, both tactile and visual, with its expected localization being medial for foot movement; the ventral premotor cortex, because of its involvement in decision making based upon somatosensory signals, activity that mirrors the actions of viewed subjects, and because of its response to externally cued stimuli.

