For ~20 minutes, participants will perform IG and EG sequences of foot-tapping movements inside the scanner using established methods . As such, the task will involve unilateral ankle dorsiflexion, to a maximum of 30° in a wooden apparatus with movements blocked by IG or EG condition. Participants will be provided foam padding and towels to restrain head motion. Participants’ knees will be flexed to approximately 135° with a soft roll under the knees. An assistant will verify task performance timing and amplitude, as well as monitor for synkinesia from the other limb. If the patient is unable to keep the other limb still, the data will be excluded. Based on pilot scans that we recently collected in 15 individuals with stage II and III PD, we expect 20% attrition for excessive head movement. However, these participants were scanned while ON meds, which generally increases the presence of dyskinesia. Because we will a) test participants OFF meds, b) screen for excessive head and lower limb tremor, and c) target recruitment in order to account for 20% attrition, we expect to retain a sample size that will allow us to detect effects and make meaningful comparisons. Ankle range of motion will be recorded with an MR-compatible potentiometer and amplitude will be averaged over each condition. Absolute timing error will be determined by the potentiometer also, by comparing the timing of every other change in acceleration, with the ideal timing sequence. Thus, the time course of changes in acceleration will be effectively considered the timing of the participants’ taps. Error will be averaged from the accumulated absolute value of the tapping errors which either over- or under-shoot the ideal timing. Tapping will occur at a frequency of 0.5 - 2 Hz, *IRB 60613 Motor Training in PD*

Activation paradigm: In 30 s EG blocks, participants will tap their feet in response to externally provided auditory cues. In 30s IG blocks, participants will tap their feet in pre-learned rhythms. 21 s of rest will occur between IG and EG blocks. There will be 5 blocks per condition

given that individuals with PD demonstrate marked tapping performance deterioration above 2 Hz, in terms of increased movement rate, decreased amplitude and loss of movement phase.

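### Aim 1 defines the IG and EG circuits from separate task-versus-rest maps, so the healthy-control claim of task-specific networks is not tested by any stated comparison of IG with EG

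*Combined protocol and SAP*

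**What the plan says.** Hypothesis 1 (section 4) makes a claim about specificity: "In healthy controls, IG and EG foot-tapping are related to task-specific neural networks", with the striato-thalamo-cortical circuit (STC) assigned to IG and the cerebello-thalamo-cortical circuit (CTC) to EG.

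The analysis is in section 7, Statistical Analysis Plan for Aim 1. At subject level, "activation maps for the IG and EG tasks versus rest will be determined for each subject on a voxel by voxel basis". At group level, "First level contrast maps (betas) for the IG and EG tasks versus rest derived in each subject will be submitted to a second-level, random-effects analysis". The resulting maps are thresholded at p < .05, "corrected for multiple comparisons using the false discovery rate (FDR) method". The rule follows: "These activation maps will be used to define circuitry for IG and EG foot-tapping". The primary outcome, percent signal change, is also taken relative to rest.

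On the task itself, the Experimental Plan says "the task will involve unilateral ankle dorsiflexion, to a maximum of 30° in a wooden apparatus with movements blocked by IG or EG condition". Each foot is tested under both conditions, in 30 s movement blocks separated by 21 s of complete rest. Only EG has the auditory cue.

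The Power Analysis for Specific Aim 1 says an ANOVA will distinguish the circuits. It lists no factors and sizes only a between-subjects effect: f = 0.45, F(1,38) = 4.098, power 0.80.

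For Aim 2, Hypothesis 3, seed regions are placed at centres of "clusters of activation in the group level activation maps for IG and EG foot-tapping", within named STC and CTC areas.

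**The concern.** That a network is task-specific is a statement about the difference between two tasks. The stated rule never uses that difference. It asks twice whether a task exceeds rest, and rest contains neither movement nor cue.

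The plan's own rationale shows why this matters. Among its reasons for the STC list is "the primary motor cortex, because of its activation during foot movements". Rostral SMA is partly justified by activation during foot flexion and extension, and the cerebellar lobules on the CTC list by activation during cued foot movement in controls. Primary somatosensory cortex is expected at its medial foot location. So both lists contain areas likely to exceed rest whenever the foot moves.

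At stake is the meaning of the labels. An area active in both tasks would be listed in both circuits although it says nothing about guidance. An area just above the threshold in one map and just below it in the other would look specific to one task without evidence that the tasks differ there.

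**Working it through.** **1. The plan's own figure.** For a two-group F test with N = 40 and f = 0.45, the noncentrality is f² × N = 0.2025 × 40 = 8.1. The critical F(1,38) at 5% is 4.098, as stated, and power is 0.792 against the stated 0.80. The figure reproduces as a plain PD-versus-control comparison. The degrees of freedom do not settle which effect is meant: in a 2 × 2 mixed ANOVA with N = 40, the task effect and the group-by-task interaction also have 1 and 38 df. Only the plan's description of the effect as between subjects identifies it.

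**2. Entry into one map.** Assume n = 20, a movement effect d (mean over SD, versus rest) equal in both tasks, and a one-sided voxel cut-off standing in for the FDR threshold. The documents give neither d nor the cut-off that FDR would produce. Power is P(T > t_crit), where T is noncentral t with 19 df and noncentrality d√20.

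| d | p = .005 | p = .001 |
|---|---|---|
| 0.8 | 0.754 | 0.517 |
| 1.0 | 0.932 | 0.792 |
| 1.2 | 0.989 | 0.943 |

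**3. Entry into both maps, or only one, with zero IG-EG difference.** Simulation with n = 20, 20,000 replicates per setting and an assumed IG-EG correlation of 0.3 to 0.9. Ranges are over the correlation.

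| d | Both, p < .001 | Only one, p < .001 | Both, p < .01 | Only one, p < .01 |
|---|---|---|---|---|
| 0.5 | 3-9% | 9-20% | 20-33% | 15-40% |
| 0.8 | 31-44% | 16-42% | 72-79% | 9-23% |
| 1.0 | 65-74% | 11-29% | 93-95% | 3-6% |
| 1.5 | over 99% | under 1% | about 100% | about 0% |

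A strong movement response puts the area in both maps; a moderate one often puts it in one only. A paired IG-minus-EG test on the same data fires at its nominal rate: about 5% at .05 and about 0.1% at .001. These rates should be compared at like thresholds; a 5% uncorrected test is not the counterpart of a map cut at .001.

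**4. What a direct contrast could detect.** Paired t test, assumed standardised difference dz = 0.5, noncentrality 0.5√n (2.236 for n = 20; 3.162 for n = 40).

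| Threshold | n = 20 (controls alone) | n = 40 (both groups pooled) |
|---|---|---|
| two-sided .05, uncorrected | 0.56 | 0.87 |
| one-sided .005 | 0.30 | 0.67 |
| one-sided .001 | 0.13 | 0.45 |

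**The case against.** The strongest reply is that an IG-EG comparison is intended. The ANOVA is said to distinguish the circuits, every participant supplies both values, and F(1,38) fits a task effect as well as a group effect. This stands to the extent that the degrees of freedom do not exclude a task factor. But none is written down, and the rule defining the circuits operates before any ANOVA.

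The section 5 rationale also frames part of the control prediction relative to rest, and the maps do answer that part. They do not answer the claim of task-specificity in section 4.

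Three stronger readings are tempting, and the documents do not support them:

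- A reader might infer that any working motor task would confirm Hypothesis 1 in controls. If movement drives both maps, both circuits appear in both, and that visible overlap argues against the hypothesis.
- A reader might infer that the PD findings fail too. That half of Hypothesis 1 compares PD with controls, and movement activation common to both groups largely cancels.
- A reader might infer that the Aim 2 seeds are invalid. They are confined to named areas, so anatomy assigns the circuit and the map supplies only the location.

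Nor are all eight areas chosen for responding to foot movement. The putamen, both thalamic areas and ventral premotor cortex are justified on other grounds, and SMA and somatosensory cortex only partly on that one.

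**Conclusion.** The concern holds in a limited form. Followed as written, Aim 1 shows which areas are active during each task, but it does not test whether IG and EG tapping use different networks in controls. Areas such as primary motor cortex, the cerebellar lobules and probably primary somatosensory cortex can enter both maps, or one by chance, with no true task difference.

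That the comparison is missing follows from the text alone. How often the labels would mislead depends on assumed movement effects, correlations and cut-offs: under the settings tried at n = 20, entry into both maps ranges from 3% to almost 100%. The effect on PD-versus-control comparisons is small. For the seeds, the limit is on how they may be described.

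**What to change.** In section 7, Power Analysis and Statistical Analysis Plan for Aim 1:

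- Keep the versus-rest maps, described as showing activation.
- Pre-specify the within-subject contrasts IG>EG and EG>IG, per foot, from the same first-level model, masked to voxels active versus rest in at least one task.
- Specify a group (PD, control) × task (IG, EG) mixed ANOVA on percent signal change in the named STC and CTC areas. State its factors.
- Call an area IG- or EG-specific only if the task difference is significant. Report areas active in both tasks without a demonstrated difference as shared. Absence of a significant difference does not show equality.

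In the connectivity section for Aim 2, Hypothesis 3, the seeds may stay in the named areas but should not be described as task-specific unless the contrast supports it.

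The cost is wording and extra contrasts from a model that already holds both regressors; no new data are needed. The plan should state the downsides. Fewer areas will qualify. Power in controls alone is modest: about 56% at an assumed dz of 0.5 (two-sided .05, uncorrected) and about 30% at one-sided p = .005. EG>IG also contains the auditory cue and any difference in tapping rate, so auditory areas should not be read as guidance effects and tapping rate should be considered as a covariate.
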